TITLE: Effects of Choline Supplementation on Fetal Growth in Gestational Diabetes Mellitus

BACKGROUND AND SIGNIFICANCE

Macrosomia resulting from gestational diabetes mellitus (GDM) has long-lasting influence on health

GDM, characterized by glucose intolerance that develops during pregnancy, is a major public health problem affecting up to 15% of pregnancies in some populations(1). The prevalence of GDM has increased by 10 – 100% in different populations in recent years, partly due to the obesity epidemic (20, 21). GDM increases direct medical cost by over 40% compared to healthy pregnancies (22, 23). A major adverse birth outcome of GDM is macrosomia, defined as a birth weight higher than 4kg, occurring in 20% of GDM versus 10% of non-GDM pregnancies (22). Macrosomic neonates are prone to childhood obesity, hypertension, and diabetes across the life-course (2-6). ***Addressing macrosomia at birth could be one of the most cost-effective ways to mitigate the fetal origin of cardio-metabolic diseases in adulthood.***

Calorie control and weight management alone cannot effectively improve fetal growth outcomes

Medical Nutrition Therapy (MNT) is a cornerstone for GDM management. The American Diabetes Association guidelines of MNT for GDM are focused on caloric intake and weight management of the pregnant women to improve their glycemic control (24). However, in studies among 600 – 1,500 pregnancies, using lifestyle interventions based on the current guidelines failed to reduce macrosomia despite improvements in appropriate gestational weight gain and dietary glycemic load of the pregnant women (8-12). These results ***imply that therapy targeted to improve maternal health is not always sufficient to benefit the fetus.*** Moreover, approximately 50% of pregnant women are not able to achieve appropriate weight gain during pregnancy (25) and approximately 20 % (26) of pregnant women with GDM are not able to make blood glucose under control due to obesity, excessive maternal weight gain, lifestyle factors, and other reasons. These concerns warrant a ***simple regimen that can be easily adopted by expecting mothers and specifically targeted to normalize fetal growth, so as to minimize the risk of fetal overgrowth and excess adiposity at birth.***

Restoring placental transport is critical for normalizing fetal growth in GDM

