In summary, there is no current effective approach to prevent GDM-related fetal overgrowth. We demonstrated that choline sufficiency was critical for restoring normal placental transport and preventing fetal overgrowth in GDM mice. If similar effects of choline could be validated in humans, the practical impact would be remarkable because currently less than 10% of pregnant women in the U.S. consume the recommended 450 mg/d Adequate Intake of choline (47). Choline is readily available in common foods such as eggs, beans, and meat and is easy and safe to provide via a choline-rich diet or choline supplements. When used in clinical trials, choline supplementation was well tolerated and was not associated with any serious adverse events.

STUDY OBJECTIVES

Specific Aim 1: Determine the effect of MCS during pregnancy on birth weight in GDM.

Specific Aim 2: Determine the influence of MCS on macronutrient transport and epigenetic modifications in the placenta and cord blood.

HYPOTHESIS

Aim 1: We hypothesize that the choline group would have lower birth weight and fewer LGA neonates than the non- choline group.

Aim 2: We hypothesize that the choline group would reduce placental transport and increase DNA methylation of metabolic genes.

STUDY DESIGN

Subjects: A convenient sampling methodology will be adopted. We will recruit pregnant women diagnosed with GDM during the second trimester of pregnancy on a rolling basis. Block randomization will be conducted based on treatment methods (i.e. insulin therapy, oral hypoglycemics, or diet only) to randomly assign participants to the intervention and control groups. Recruitment will be conducted using the following methods: (i) study flyers will be posted

at the prenatal clinic; (ii) the principle investigator and her fellows will identify pregnant women who are potentially eligible by reviewing medical records. All these patients are routinely seen by members of the MFM team fellows. The PI or co-I will introduce the study to potential participants.

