Eligibility Criteria: The inclusion criteria include GDM pregnant women before gestational week 28. GDM is diagnosed with the 2-step process: blood glucose higher than the 140 mg/dL cut-off value after 50 g non-fasting 1-hr and 100 g 3-hr oral glucose challenges. Pregnant women are qualified to participate if they are English- or Spanish- speaking, over 18 years of age, having singleton pregnancy, intending to deliver their babies at Maimonides and are without any of the conditions listed in the exclusion criteria. Exclusion criteria include pre-existing hyperglycemia, diabetes, cardiovascular conditions and liver disease prior to pregnancy. Patients may choose to participate in the study and not donate a biopsy of their placenta or umbilical cord. Patients who desire stem cell donation or storage will not be able to donate a biopsy of their placenta or umbilical cord. These patients will not be excluded from the primary analysis.

Design and Data Collection Procedures:

All interaction with participants will occur at Maimonides while sample analyses will occur at Brooklyn College (where the co-I's lab is located). The PI or co-I will obtain written informed consent from the pregnant women before study entry. Randomization will be done by pharmacy after patient signs consent. It will be block randomization of 10 patients. After randomization, the PI or co-I will provide the participant in the intervention group with choline supplement pills containing 500 mg of choline bitartrate (235 mg choline, Douglas Lab). The participant will consume 2 pills per day to obtain 470 mg choline for 8 weeks. The recommended intake of choline in the form of Adequate Intake (AI) is 450 mg/d for pregnant women and the Tolerable Upper Intake Level (UL) is 3500 mg/d. Since less than 10% pregnant women reach the AI of choline intake and the upper quartile of choline intake is below 900 mg/d (48). The dosage we provide plus the habitual intake of choline in these pregnant women will fall between the AI and UL, i.e. sufficient but not exceeding the limit. The participants in the control group will receive a placebo that contains corn oil. Both groups will also receive standard prenatal multivitamins and 200 mg/d DHA provided by the study group. We will provide the participants with 5 weeks supply of supplements and we will verify their compliance during the time with daily check-off logs of supplement consumption and leftover pill count during their next visit.

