Data Analysis: *Specific Aim 1: Determine the effect of maternal choline supplementation (MCS) during pregnancy on birth weight in GDM.* To achieve this aim, we will compare the birth weight as well as incidence of LGA between the intervention versus control group. We will also assess the influence of MCS on blood and placenta choline metabolite status, as well as the correlation between total choline intake (diet + supplement) or choline metabolite status and birth weight.

Dietary intake assessment: As mentioned above, dietary intake data collected from 3-day dietary recalls will be analyzed by the NDSR software (54, 55). Daily intakes of total choline will be calculated by multiplying the frequency of consumption by the sum of choline derivatives including free choline, phosphatidylcholine (PC), glycerophosphocholine (GPC), phosphocholine, and sphingomyelin of each food item(56). Daily intakes of betaine (the oxidation product of choline) will be calculated by multiplying consumption frequency and

betaine content of each food. Average daily intakes will be calculated as the average daily consumption of total choline and betaine over the 3 days of dietary recalls.

Measurements of choline metabolites: Free choline, betaine and other choline derivatives [e.g. PC, GPC, lysophosphatidylcholine, dimethylglycine, trimethylamine oxide (TMAO)] will be measured in maternal plasma using liquid chromatography (LC)-mass spectrometry (MS) /MS (57, 58) as was conducted in previous studies. **To ensure the accuracy and reproducibility of data**, stable isotope labeled standards will be used in extraction, all samples will be quantified based on a 6-point standard curve, and each sample will be run in duplicate. Samples with a coefficient of variation (CV) % higher than 5% within run or 10% between run will be rerun.

Specific Aim 2: Determine the influence of MCS on macronutrient transport and epigenetic modifications in the placenta and cord blood. To achieve this aim, we will determine expression of fat and glucose transporters, as well as the upstream regulating pathways AKT/mTOR in placental biopsies from the participants. We will measure the site-specific DNA methylation of key growth and metabolism related genes in the placenta and cord blood.

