Sample Size: We anticipate a 10% dropout rate due to reasons such as participants moving out of the city, pre-term deliveries, or missed placental collection. Therefore, we expect to have at least 27 sets of complete data in each group. A statistical power analysis was performed for sample size estimation accounting for rates of dropout and missing data, based on data from a randomized controlled trial of choline supplementation which demonstrates that 2 x recommended intake of choline for 12 weeks is sufficient to increase plasma choline and alter placental global DNA methylation. The initial sample size of n=30/ group will allow detection of a >20% difference in birth weight, plasma choline and placental DNA methylation at $\alpha < 0.05$ and power = 80%.

Expected Outcomes: The successful completion of this study will provide valuable insights into the use of choline supplement as a modifier of placental macronutrient homeostasis in GDM to improve fetal growth outcomes.

Timetable:

	Quarter 1	Quarter 2	Quarter 3	Quarter 4
Participant Recruitment	n = 20	n = 20	n = 20	
Sample and Data Collection				
Choline measurements		Aim 1	Aim 1	Aim 1
Gene expression and epigenetic measurements		Aim 2	Aim 2	Aim 2
Data analysis				Both Aims
Result dissemination				Both Aims

We expect to complete recruitment by the end of the third quarter and complete dietary record, clinical information, and biosample collection in the middle of the fourth quarter. We will start analytical measurements once we obtain at least a third of the samples. We expect to complete analytical measurements by the end of the year. We will analyze and disseminate data in the last quarter.

Data Safety Committee Team Plans:

Randomization is a block randomization of 5 patients. After every block of randomization, the research team with a pharmacist and at least one external physician outside of the research team [[name]] will analyze the data to ensure that there are no unanticipated adverse effects via ultrasound fetal growth patterns. If unanticipated effects are found, we will report to IRB as per policy.

REFERENCES

1. Ferrara A. Increasing prevalence of gestational diabetes mellitus: a public health perspective. *Diabetes Care*. 2007;30 Suppl 2:S141-6. doi: 10.2337/dc07-s206. PubMed PMID: 17596462.

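### Does the single figure of more than 20% misstate what 27 to 30 women per group can detect for birth weight?

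*Combined protocol and SAP*

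**What the plan says.** Study Objectives gives Specific Aim 1 as: "Determine the effect of MCS during pregnancy on birth weight in GDM". For that aim, Data Analysis says "we will compare the birth weight as well as incidence of LGA between the intervention versus control group". It does not name the test.

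The Sample Size section is the only place where the number of women is justified. It expects 10% dropout, so that "we expect to have at least 27 sets of complete data in each group". Its power basis is a choline trial described by two results: "2 x recommended intake of choline for 12 weeks is sufficient to increase plasma choline and alter placental global DNA methylation". It then concludes: "The initial sample size of n=30/ group will allow detection of a >20% difference in birth weight, plasma choline and placental DNA methylation", at alpha below 0.05 and 80% power. No SD, coefficient of variation (CV), control mean, test or sidedness is given for any of the three outcomes.

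Two other places bear on the point. Under Eligibility Criteria, of women who give no placental or cord biopsy: "These patients will not be excluded from the primary analysis". The birth-weight comparison may therefore keep more than 27 per group. Background and Significance gives the only figures on the birth-weight distribution, describing macrosomia as "defined as a birth weight higher than 4kg, occurring in 20% of GDM versus 10% of non-GDM pregnancies".

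**The concern.** A power statement normally tells the reader the smallest effect that a design can reliably find. Read that way, one figure of 20% can hold for three such different outcomes only if all three have the same CV. For birth weight that CV would have to be about 26% to 27%, an SD near 850 to 885 g, which looks too wide. With a narrower spread, 20% is some 700 g or more, well beyond what 30 per group need.

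If the figure is off, the only sample-size statement for the Aim 1 outcome would not tell a reader which birth-weight effects the trial can find, or how much a non-significant result rules out. It would also leave unclear how 30 per group was reached.

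**Working it through.** **Inputs from the documents.** 30 per group randomised; 10% dropout; 27 per group with complete data; alpha 0.05; power 80%; 20% of GDM births above 4 kg.

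**Inputs assumed here.** Two-sided two-sample t test; normal birth weights; SD of 400, 500 or 600 g. The documents give no SD.

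**The plan's own figures.** The dropout step reproduces: 30 × 0.9 = 27. The figure of 20% can be neither reproduced nor refuted, because no SD or CV is given for any of the three outcomes.

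**Step 1: the 80%-power limit in SD units.** From the noncentral t distribution, the limit is 0.777 SD at 27 per group and 0.736 SD at 30.

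**Step 2: the CV at which 20% is exactly that limit.** CV = 0.20 / limit:
- 27 per group: 0.20 / 0.777 = 25.7%
- 30 per group: 0.20 / 0.736 = 27.2%

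To turn this into grams, take the mean from the share above 4 kg: mean = 4000 − 0.8416 × SD. Setting 0.20 × mean = limit × SD gives SD = 800 / (limit + 0.2 × 0.8416):
- 27 per group: 800 / (0.777 + 0.168) ≈ 846 g
- 30 per group: 800 / (0.736 + 0.168) ≈ 885 g

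**Step 3: narrower spreads.** The mean comes from the same formula.

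| Assumed SD | Mean | 20% of mean | Limit, n = 27 | Limit, n = 30 | Power for 20%, n = 27 | Smallest n per group for 20% |
|---|---|---|---|---|---|---|
| 400 g | 3663 g | 733 g | 311 g (8.5%) | 294 g (8.0%) | >0.999 | 6 |
| 500 g | 3579 g | 716 g | 388 g (10.9%) | 368 g (10.3%) | 0.999 | 9 |
| 600 g | 3495 g | 699 g | 466 g (13.3%) | 441 g (12.6%) | 0.987 | 13 |

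As an example of the limit column, 0.777 × 600 = 466 g, and 466 / 3495 = 13.3%. The 20% difference is 1.5 to 2.5 times the limit (699 / 466 = 1.5; 733 / 294 = 2.5).

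**Step 4: sensitivity to the mean.** With the mean set freely at 3200 to 3600 g and the SD at 400 to 600 g, the limit runs from 8.2% to 14.6% of the mean. The lowest power for a 20% difference is 0.970 (27 per group, mean 3200 g, SD 600 g).

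**Step 5: sensitivity to the test.** A one-sided test has lower limits, 0.686 SD at 27 per group and 0.650 SD at 30. It makes the trial more sensitive, so the sentence stays on the safe side.

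**Step 6: what this says about the sentence.** The plan says that a difference above 20% can be detected with 80% power. In every case of Steps 3 to 5, power for 20% exceeds 80%. The statement fails for an outcome only if its CV is above about 26% (27 per group) or 27% (30 per group). The documents give no birth-weight figure that shows this.

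**The case for a change.** The strongest case for acting is that a statement can be true and still tell the reader little. If 20% was chosen for plasma choline or methylation, the trial's sensitivity for birth weight is stated nowhere, although birth weight is the Aim 1 outcome. The macrosomia rates sharpen this. Under normality and a common SD, a shift from 20% to 10% above 4 kg is z(0.90) − z(0.80) = 0.44 SD, for which power is about 35% at 27 per group and 39% at 30. A reader who sees only the 20% figure could take a null result as evidence against choline.

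Part of this stands. The birth-weight SD, its source, the test and the detectable difference in grams are absent, and stating them would be good reporting.

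The rest does not carry a change. The 20% and 10% rates are background figures for GDM and non-GDM pregnancies, and the plan sets no aim of moving from one to the other. The 0.44 SD also depends on the common SD: with SD ratios of 0.9 to 1.1 between the groups it becomes 0.31 to 0.57 SD, and power 22% to 54%. What a null result rules out is read from its confidence interval, whose expected 95% half-width is about 0.55 SD at 27 per group and 0.52 SD at 30, whatever this sentence says.

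The source trial is cited for global methylation, while Data Analysis for Aim 2 says "We will measure the site-specific DNA methylation of key growth and metabolism related genes in the placenta and cord blood". That is a separate question and has no bearing on birth weight.

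**Conclusion.** The concern does not call for a change. At assumed SDs of 400 to 600 g, with the mean fixed by 20% of births above 4 kg, the trial has 80% power for about 290 to 470 g (8% to 13%) and at least 98.7% power for a 20% difference. It is more sensitive to birth weight than the sentence claims, and it does not miss its stated power.

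This rests on SDs that the documents do not give. They do not exclude an SD near 850 to 885 g, but at that SD 20% would simply be the 80%-power limit, and the sentence would still hold.

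What remains is missing detail, which an analyst can supply from the SD seen in the trial when reporting. It alters no enrolment, visit, assay, analysis set or result.

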The participants will come in for a total of 3 visits at times of routine clinical care. The first visit will be at 28 weeks of gestation when we enroll the participants, the second visit will be at

32 weeks of gestation, and the third visit will be at 36 weeks. There are additional routine clinic visits (e.g., at 32 weeks) during which information can be obtained if a patient missed a study visit. We will collect a baseline questionnaire at the first visit (approximately 20 minutes), conduct 3-day dietary recalls after the first visit (approximately 20 minutes, each), and check current weight and collect 20 mL blood samples at all visits. At delivery, we will collect placenta samples and cord blood from the participants (**Figure 3**).

Baseline questionnaire: The questionnaire includes demographic and medical information such as age, due date, ethnicity, parity, marital status, education level, occupation, household income, medical insurance, substance use, medication use, nutrition supplement, family history of chronic diseases, and self-reported pre-pregnancy weight.

[figure not shown]

Figure 3. Study design

Dietary assessment: Three 24-hr dietary recalls, 2 on weekdays and 1 on a weekend day, will be obtained from each participant by a trained research assistant (RA) via phone calls following the first visits to quantify dietary choline intakes. The multi-pass method of Harnack and colleagues will be used (49). This method is widely used in dietary recall data collection for research (e.g. National Health and Nutrition Examination Survey) and **validated for its accuracy in assessing dietary intake (50)**. The RA will record food identification, quantity, ingredient specification, preparation method and enter data into the Nutrition Data System for Research (NDSR) software to analyze choline intake. The RA will also ask participants about their **physical activity (PA)** during the past 24 hours using the PA recall instrument (51).

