Anthropometric measurements and blood collection: We will measure the participants' weight and height using a medical weighing scale with mechanical height rods during the visits. To minimize food-related concentration differences in plasma biomarkers, participants will be instructed not to consume food for at least 4 hours before their blood draw in the morning. This is a standard recommendation for prenatal visits and is considered as safe (52, 53). We will also have preventative measures such as an examination bed to rest in and juices, food, and water should the women need them. About 20 mL of fasting venous blood will be drawn from each participant during the visits by a fellow/resident/nurse. Blood samples will be collected into one EDTA blood collection tube and one serum separator tube and centrifuged to obtain plasma, buffy coat, and serum. Samples will be processed and stored at -80°C at Brooklyn College until being used for analytical measurements.

Blood glucose management: We will obtain information about fasting glucose, hemoglobin A1C, medication and insulin therapy from medical charts of the participants.

Birth information and sample collection at delivery: The participants will notify the PI or co-I when they are admitted to the birth center by phone. We will also send them reminders as their due dates are approaching. In addition, **the birth center medical staff will be given a list of participant names, thus they will also contact the PI or co-I if a participant checks in when none of the study staff is on site.** The research team will be available 24/7. Once the baby is delivered, we will collect two tubes of cord blood to retrieve serum, plasma, and buffy coat. We will measure the size and weight of the placenta and process the placenta using the following method: full-thickness placental biopsies will be obtained using a 6-mm Keyes punch and stabilized in RNeasy[®] (for RNA), or frozen in liquid nitrogen (for other purposes). Samples will be transported to the co-I's lab for long-term storage at -80C before use.

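### The protocol names no adverse event, symptom or complication item to collect, and its only stated safety signal, ultrasound fetal growth, cannot reveal harms other than growth.

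*Combined protocol and SAP*

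**What the plan says.** **Safety review.** Data Safety Committee Team Plans provides for a review after every randomization block by the research team, a pharmacist and at least one physician from outside the team. Its purpose is to "ensure that there are no unanticipated adverse effects via ultrasound fetal growth patterns". The consequence is stated as "If unanticipated effects are found, we will report to IRB as per policy". No other method of finding adverse effects is given.

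**Visits.** Under Design and Data Collection Procedures there is a baseline questionnaire at the first visit and dietary recalls after it. The team will also "check current weight and collect 20 mL blood samples at all visits". Adherence is checked by "daily check-off logs of supplement consumption and leftover pill count during their next visit".

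**Charts.** Under Blood glucose management: "We will obtain information about fasting glucose, hemoglobin A1C, medication and insulin therapy from medical charts of the participants".

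**Delivery.** Under Birth information and sample collection at delivery: "Once the baby is delivered, we will collect two tubes of cord blood to retrieve serum, plasma, and buffy coat". Placental size, weight and biopsies follow.

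**Hypothesis and analysis.** Aim 1 expects that "the choline group would have lower birth weight and fewer LGA neonates" than the control group. The clinical outcomes to be compared between arms in Data Analysis are birth weight and LGA.

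**Starting position on safety.** The summary that closes the Background says that in clinical trials "choline supplementation was well tolerated and was not associated with any serious adverse events".

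**The concern.** The safety section sets out to find effects that nobody expects, but the one instrument it names measures fetal growth, which is what the supplement is meant to change. Nausea or other intolerance, stopping the pills because of side effects, a maternal complication, or a newborn complication unrelated to size would not appear on a growth scan. The itemised data collection does not name any of these either.

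Two things are at stake. During the trial, the external physician would be asked to judge safety from a listing that need not contain non-growth events. At the end, the report could not describe how well the supplement was tolerated in this population, although the protocol opens with a statement about tolerability. A pill count can show that doses were missed, but it does not separate side effects from forgetting.

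**Working it through.** **Step 1: compare what is collected with what a safety review would need.**

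| Source in the protocol | Items named | Adverse event or complication item? |
|---|---|---|
| Visit 1 | Baseline questionnaire, weight, blood; diet and activity recalls afterwards | None after treatment starts |
| Visits at weeks 32 and 36 | Weight, blood | None |
| Adherence check | Daily log, leftover pills | No reason for missed pills |
| Chart pull | Fasting glucose, A1C, medication, insulin | No maternal complication |
| Delivery | Cord blood; placental size, weight, biopsies | No newborn complication |
| Data Analysis, between arms | Birth weight, LGA; laboratory markers | No safety comparison |
| Sample Size | Pre-term delivery as one reason for the 10% dropout | Treated as loss of data, not as an outcome |
| Data Safety Committee Team Plans | Ultrasound growth | Growth only |

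**Step 2: compare the safety signal with the hypothesis.** Aim 1 predicts lower birth weight. The safety signal is fetal growth. Both lie on the same axis, and the safety section gives no criterion for telling intended slowing from harmful slowing. Off that axis, the signal carries no information.

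**Step 3: check the plan's own number.** The numbers per arm come from Sample Size: 30 randomized and 10% dropout, so 30 × (1 − 0.10) = 27 complete. This reproduces the stated 27. No safety figure is stated, so there is none to reproduce.

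**Step 4: descriptive context, using assumed event rates.** The documents give no adverse event rates, so 1%, 5% and 10% are assumptions.

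The probability of at least one event among n women is 1 − (1 − p)^n.

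| True rate p (assumed) | n = 30 | n = 27 |
|---|---|---|
| 1% | 1 − 0.99^30 = 26% | 1 − 0.99^27 = 24% |
| 5% | 1 − 0.95^30 = 78.5% | 1 − 0.95^27 = 75% |
| 10% | 1 − 0.90^30 = 95.8% | 1 − 0.90^27 = 94% |

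With zero events, the one-sided 95% upper bound is 1 − 0.05^(1/n). This is 9.5% for n = 30 and 10.5% for n = 27.

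**Step 5: what recording could not do.** With a two-sided Fisher exact test at 0.05 and 30 per arm, power is about 9% for 5% versus 15%, and about 10% for 10% versus 20% (rates again assumed). A table by arm would describe events; it would rarely establish a difference.

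**The case against.** The strongest reply is that silence in this protocol proves little.

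- **The delivery list is not exhaustive.** It also omits birth weight, which the trial plainly intends to obtain because Aim 1 compares it. The section heading refers to birth information, and the Timetable text mentions clinical information without itemising it.
- **Some relevant data are collected.** Glycaemia, medication, maternal weight and pill counts are all gathered. Pre-term delivery must be noticed if it is to count as dropout. Plasma TMAO is measured.
- **Other documents may cover it.** Consent pages are removed, attachments are not shown, and the IRB policy referred to is not in the text.

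All of this stands, and it rules out two stronger readings. A reader might infer that no adverse event would be recorded at all. The text supports only that none is specified, because routine care and unlisted clinical data could bring events to light. A reader might also infer that ultrasound shows nothing except the hypothesised benefit. That goes too far: a scan could show excessive restriction or overgrowth, neither of which is the intended effect.

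A further fair objection is that seeing an event among 30 women does not attribute it to choline, since complications also occur in the control arm, and the power figures above confirm how little a comparison could show.

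None of this answers the central point. The indirect data are not designated as safety data or compared by arm for safety, and the one method the safety section does name cannot show a non-growth harm.

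**Conclusion.** The point holds for the text available. The protocol specifies no symptom or adverse event enquiry, no reason for missed pills, and no maternal or newborn complication item. Its sole named safety signal shows growth only, on the same axis as the hypothesised effect. The review as described has no planned way to reveal intolerance or harms other than growth. This is a stated method that does not match its stated purpose, so it is more than missing detail.

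The gain from correcting it is descriptive. If events were recorded, harms at an assumed 5% or 10% would probably be seen at least once in the choline arm (79% and 96% with 30 women; 75% and 94% with 27). An absence of events would bound the rate at 9.5% or 10.5%. Rare harms would usually be missed, and attribution to choline would remain weak.

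The conclusion assumes that the unseen consent pages, attachments and IRB policy do not already contain an adverse event plan. The birth-weight comparison is not affected. The change should be made, but the trial does not stand or fall on it.

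**What to change.** 1. At the existing week-32 and week-36 visits, ask every woman in both arms the same short symptom list and the reason for any missed pills.
2. From the delivery chart, abstract a named list of maternal and newborn complications. Include pre-term birth as an outcome as well as a reason for missing data.
3. At each review, give the external physician the cumulative listing by coded arm.
4. Tabulate the same items by arm in the final report, as description without a claim of power.
5. Reword Data Safety Committee Team Plans so that adverse effects are not limited to ultrasound growth. If an adverse event plan already exists in an attachment, cite it there.

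The cost is a short form at two visits that already take place, and some chart abstraction beyond the glycaemia and medication items now listed. Newborn complications in particular are additional work. No dose, schedule or sample size changes.
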